Service delivery processes: Key aspects of service delivery processes in the theory of change—goals, inputs, activities, and outputs—articulate the experiences that are designed to solve specific problems for those who agree to participate in the A-HBF Project. As a result, three broad service delivery goals are identified to maximize A-HBF Project participation benefits as explained below:

- **Goal 1 - Deliver *core curriculum* as primary services to A-HBF participants:** Candidates will understand that they receive *core curriculum* to develop healthy attitudes (partner relationship, sexual, financial, and employment) and skills to engage in healthy partner relationship behaviors, but only after receiving an orientation about the A-HBF Project and giving project staff informed consent to participate in study activities. Then, *SSHF* curriculum will be delivered as specified in the logic model.
- **Goal 2 - Deliver *support services* to A-HBF participants:** Candidates will understand that they receive *support services* based on their needs to further develop their skills to engage in healthy relationships and their financial and employment readiness, but only after receiving an orientation about the A-HBF Project and giving project staff informed consent to participate in study activities. Then, Family Coaches and Career Coaches will offer trainings and make referrals to promote further success for participants.
- **Goal 3 - Conduct Continuous Quality Improvement (CQI) to ensure full implementation of project services to participants:** Reports prepared and presented to the CQI Team by evaluators in each of the 5 steps in the CQI Process will use a series of performance indicators to track key outputs over time to identify any A-HBF services delivered to study groups that might fall short of the intended amounts to be offered (i.e., fidelity standards) and received (i.e., dosage thresholds) by them. The CQI Team will then work with project staff to develop and implement performance interventions to address any outputs that need improvement to ensure the services offered to and received by participants meet the intended amounts by the end of each program year.

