In this study, a descriptive study design will be used to determine if A-HBF participants benefit from the *Survival Skills for Healthy Families (SSHF)* curriculum. At-risk or homeless youth who agree to participate in the study will receive the *SSHF* curriculum through either a series of 7 in-school weekly workshops (14 hours) or an intensive weekend retreat co-attended by their parents (16 hours) followed two weeks later by a Reflections Workshop (2 hours). All program participants also receive support services delivered by Family Coaches and Career Coaches as needed.

Baseline data will be collected from participants shortly following study enrollment. Post-test data will be collected following curriculum completion, approximately 2-7 weeks following study enrollment depending on the curriculum delivery format. Follow-up data will be collected one year after study enrollment.

B. Methods to develop study groups

Because this is a descriptive evaluation, this subsection is not relevant.

C. Sample

The target population for this study is at-risk and homeless youth from high-need school districts in Harris County who are 14-18 years of age and enrolled in 9-12th grades. AVANCE will work with school districts, school boards, and individual schools to identify and recruit participants from the target population. The unit of analysis for this study is individual youth. See Appendix D for anticipated sample flow and attrition rates.

Power analysis:

The analysis of survey data will address the primary and secondary research questions with findings derived from running a linear regression model that quantifies the potential benefits of Building Futures Program participation and outcomes as well as the relationship of participant characteristics to Building Futures Program benefits. Benefits are quantified by specifying a model that compares the relative influences of participant characteristics as predictor that is regressed against a series of dependent variables (e.g., outcomes specified in the logic model). Given the predicted sample size as described in the appended logic model, the following calculations regarding power and effect size can be made.

	Participant Responses	Minimum Detectable Effect Size
Post-test	1105	0.017
Follow-up	774	0.023

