These power analyses assume an Alpha Level of 0.05 with a two-tailed test and power level set at 0.80 (1 – Beta). The estimated effect sizes are all small effects or nearly small effects that would be detected, based on best practices outlined by Cohen (1988) of small effect sizes <0.02 and medium effect sizes <0.15. With these analyses, the proposed research design is demonstrated to measure large, medium, and small changes in participants' responses.

Table 4: Methods to Promote Sufficient Program Participation

What methods will you use to ensure sufficient sample is recruited, enrolls, and participates in the program?	AVANCE will work with schools and their community partners to recruit program participants, and AVANCE will provide incentives for program retention and completion. The CQI process will address issues regarding program recruitment and enrollment to ensure targets are met.
Who will be responsible for recruiting the evaluation sample?	The evaluation sample will not differ from the program population, in that all participants will be invited to participate in the evaluation. Enrollment into the evaluation will be conducted by the CQI Data Manager who will conduct the informed consent process and proctor the baseline data collection efforts.

Please describe any incentives to be offered for program participation and/or completion and/or data collection and/or participation in the evaluation.

Program Participation – AVANCE will provide a series of incentives for program retention (promotional items) and completion (\$75 gift card).

Evaluation Participation – No incentives will be used for the first two data collections- baseline and post-test, while participants are beginning or still engaged in services. A \$50 incentive will be used for the 1-year follow-up survey and will be provided in the form of a Walmart gift card.

D. Lead staff

See Appendix B for CVs of lead evaluation staff.

Table 5: Lead Evaluation Staff

Name	Organization	Role in the Evaluation
[name]	Midwest Evaluation and Research	Principal Investigator
[name]	Midwest Evaluation and Research	Lead Evaluation Consultant
[name], MA	Midwest Evaluation and Research	Evaluation Project Manager
[name]	Midwest Evaluation and Research	CQI Data Manager

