On a bi-weekly basis, the CQI Data Manager, the local evaluation staff, and MER technical specialists will be responsible for downloading data from the nFORM and MER On-Line Local Evaluation (OLLE) systems for processing and presentation to the CQI team for tracking and monitoring performance measurement outcomes (recruitment, enrollment, dosage, completion, referrals, etc.) so that near real-time adjustments can be made to program implementation to ensure compliance with program goals and objectives.

All MER training is currently being recorded, and as new staff come on board with projects or project staff turnover (or need refresher training), recorded training material can be shared and accessed with follow-up one on one training with the primary local evaluator and the MER LOB Lead, who has more than 15 years' experience in evaluating HMRF projects.

Tracking participants and reducing attrition:

For each wave of data collection listed in Table 7, what is your estimated response rate?	Baseline	100% - done at the time of enrollment
	Wave 1	90% - estimated A-HFP completion rate
	Wave 2	70% - estimated 1 year follow-up rate

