### Model Specification to Predict Outcomes With Dosage

Construct by Outcome	Dependent Variables (follow-up)	Response Codes for Dependent Variables	Dependent Variable Type	Independent Variables
Primary outcome:				
Partner Relationship Behavior: 6 scaled items	DISAG_BE_FU	1 = none of the time to 5 = all of the time	Continuous	Dosage of curriculum; co-variates (using pre-survey scores)
5 scaled items	REL_BE_FU	1 = I am extremely good at this to 4 = I am extremely bad at this		
Secondary outcomes:				
Partner Relationship Attitudes: 9 scaled items	PARTREL_ATT_FU	1 = strongly agree to 4 = strongly disagree	Continuous	Dosage of curriculum; co-variates (using pre-survey scores)
3 scaled items	PARTREL_FUT_ATT_FU	1 = almost no chance to 5 = almost certain		
Sexual Attitudes: 7 scaled items	SEX_ATT_FU	1 = strongly agree to 4 = strongly disagree		
Financial Attitudes: 4 scaled items	FIN_ATT_FU	1 = strongly disagree to 7 = strongly agree		
Employment Attitudes 4 scaled items	EMP_ATT_FU	1 = strongly disagree to 7 = strongly agree		

Step 4 – run the linear regression model: Procedures to run the linear regression model are influenced by dependent variable types. Standard regression is necessary to model the influence of curriculum dosage on continuous dependent variables, such as when participants respond to

---

multiple items in a scaled construct by indicating levels of agreement with statements about key partner relationship attitudes.

Step 5 – interpret model results: Model results demonstrate the benefits of A-HBF participation whenever dosage variables predict more positive primary and secondary outcomes for a construct. For primary outcomes, benefits of receiving *SSHf* curriculum confirm hypotheses when respondents with higher levels of participation more frequently report ( $p < .05$ ):

1. Healthy partner relationship behavior

For secondary outcomes, benefits of receiving *SSHf* curriculum confirm hypotheses when respondents with higher levels of participation more frequently report ( $p < .05$ ):

2. More positive attitudes about partner relationships
3. More positive attitudes about sexual relationships
4. More positive attitudes about financial readiness
5. More positive attitudes about job readiness

---

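### The power section's claim to detect small changes does not carry over to the one-year dosage test, which under 90% completion needs a full-course benefit of roughly 0.3 to 0.7 residual SD

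*Protocol*

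**What the plan says.** Protocol II.C (Sample, Power analysis) says that the research questions will be answered with "findings derived from running a linear regression model that quantifies the potential benefits of Building Futures Program participation". The printed rows are "Post-test 1105 0.017" and "Follow-up 774 0.023". The basis is given as "These power analyses assume an Alpha Level of 0.05 with a two-tailed test and power level set at 0.80". The section then states that "the proposed research design is demonstrated to measure large, medium, and small changes in participants' responses". It names no effect-size scale, number of predictors or distribution of hours.

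SAP IV.A plans two kinds of analysis. One is a repeated-measures ANOVA of pre-survey against 12-month follow-up. The other is regression on curriculum hours. Under the model specification for dosage, with follow-up scores as dependent variables and p < .05, Step 5 says: "Model results demonstrate the benefits of A-HBF participation whenever dosage variables predict more positive primary and secondary outcomes for a construct".

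Two other places bear on how much hours will vary. Protocol III.A (Tracking participants and reducing attrition) expects "90% - estimated A-HFP completion rate" and a 70% one-year follow-up rate. Protocol I.C, Goal 3, commits the quality-improvement process to "ensure the services offered to and received by participants meet the intended amounts by the end of each program year".

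**The concern.** A regression slope on hours can be detected only as far as hours differ between youths. A small share of variance explained means a small benefit of the full course only if hours are widely spread. This programme aims for nearly everyone to receive the full amount, so the same variance share corresponds to a much larger benefit.

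The consequence lies in interpretation. Step 5 treats a significant dosage slope as confirming each hypothesis. If the programme truly produces a modest full-course benefit, the slope will often be non-significant. A reader told that the design has 80% power for small changes would then take that result as evidence of no benefit.

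**Working it through.** **Inputs from the documents.** Two-sided alpha 0.05, power 0.80, N=1105 and 774, printed effects 0.017 and 0.023 (Protocol II.C). Completion 90%, one-year response 70% (Protocol III.A). Full course 14 hours weekly, or 16 hours plus a 2-hour workshop for the retreat (Protocol II.A).

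**Assumptions, not in the documents.** Linear dose-response; non-completers' hours as shown below; completers at full hours unless stated; the pre-score correlation r; 0.2 and 0.3 SD as illustrative modest benefits.

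**1. The printed figures.** II.C's cut-offs of 0.02 and 0.15 match Cohen's f-squared. For an overall F test with noncentrality f² × N, solving for 80% power gives:
- 13 predictors: 0.0163 (N=1105) and 0.0234 (N=774)
- 14 predictors: 0.0168 and 0.0241
- one predictor: 0.0071 and 0.0102

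The printed pair therefore fits an overall test with about 13 or 14 predictors, to within rounding.

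**2. The time effect.** The detectable mean change, in SDs of the change score, is (1.960 + 0.842)/√774 = 2.802/27.82 = 0.10.

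**3. The dosage slope.** Let d be the share of the course received and D the full-course benefit in residual SDs. Then f² = D² × Var(d), and the detectable D for a one-coefficient test is 0.1007/SD(d). Power is Φ(D × SD(d) × √774 − 1.96). With 90% at d=1:
- Non-completers at zero: Var = 0.9 × 0.1 = 0.09, SD 0.30.
- Spread evenly over 0-100%: mean 0.95, E[d²] = 0.9 + 0.1/3 = 0.9333, Var = 0.9333 − 0.9025 = 0.0308, SD 0.176.
- All at half: Var = 0.09 × 0.25 = 0.0225, SD 0.15.

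| Non-completers' hours | SD(d) | Detectable D | Power at 0.2 SD | Power at 0.3 SD | D at printed f² = 0.023 |
|---|---|---|---|---|---|
| None | 0.30 | 0.34 | 39% | 71% | 0.51 |
| Even, 0-100% | 0.176 | 0.57 | 16% | 31% | 0.86 |
| Half | 0.15 | 0.67 | 13% | 24% | 1.01 |

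**4. What moves the range.**
- *Pre-score adjustment.* In outcome SDs, multiply by √(1 − r²). At r=0.5 (factor 0.866) the thresholds become 0.29, 0.50 and 0.58. In the most favourable case, power at 0.2 SD is then about 49%. At r=0.7 that case still needs 0.24 SD.
- *Completers who miss sessions.* If completers spread evenly over 50-100% of hours and non-completers over 0-50%, SD(d) is 0.208 and the threshold 0.48. With an 80% cut-off it is 0.57.
- *No format adjustment.* If 10% to 50% of youth take the 18-hour format and non-completers' hours are spread evenly, the threshold is about 0.51 down to 0.41 per 14 hours.
- *Mainly completers followed.* 0.70 × 1105 = 773.5, so 774 looks like 70% of the post-test respondents, and Protocol III.A limits the post-test to those who complete. Applying 70% to the implied enrolment of 1105/0.9 ≈ 1228 would give about 860. With completers only, spread evenly over 50-100% of hours, SD(d) = 0.5/√12 = 0.144 and the threshold is 0.70. Over 80-100%, SD(d) = 0.058 and the threshold is about 1.7.
- *Non-completers who attend most of the course.* If all of them receive 75%, the threshold is 1.34.

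**The case against.** The best defence is that II.C never mentions hours. It names participant characteristics as predictors and makes its claim for the design as a whole. The hypotheses concern change after participation, and the SAP plans the pre versus 12-month ANOVA for exactly that. This stands in part: the time effect does not depend on the spread of hours, so a reader should not infer that the study cannot detect small changes at all. It does not rescue the dosage slope, because II.C describes a regression on participation and Step 5 confirms hypotheses from dosage.

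A second defence is that no printed number has been shown to be wrong. That is correct, since 0.017 and 0.023 reproduce approximately. The fault is in what is concluded from them.

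A reader might also infer a firm floor of about 0.6 SD, or almost no spread in hours. The documents support neither. They give no hours for non-completers and no attendance threshold for completion, and on the same 90% figure the threshold is 0.34 residual SD if non-completers attend nothing. A spread of 0.15 to 0.30 of a course is narrow but not negligible, and the quality-improvement goal is an aim rather than an attendance distribution.

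Finally, format adjustment is stated for the pre-to-post dosage model, while the table for the one-year model lists only dosage and pre-survey scores as covariates. The within-format figures are therefore an assumption for that model. The numbered steps before Step 4 and the appendices were not in the text available to me and may say more.

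**Conclusion.** Wrong as written, in one respect: the stated sensitivity to small changes is not a property of the one-year dosage test. At N=774 with 90% completion, within format and all non-completers followed, that test needs a full-course benefit of roughly 0.3 to 0.7 residual SD for 80% power. Its power for 0.2 SD is about 13% to 39% before any gain from pre-scores. The range assumes a linear dose-response, completers at full hours, and non-completers averaging half the course or less. It falls to about 0.29 to 0.58 outcome SD at an assumed pre-score correlation of 0.5, is also lower without format adjustment, and rises to about 0.7 to 1.7 if mainly completers are followed, as the projected count suggests. In none of the cases worked here does the dosage test reach 80% power for 0.2 SD. The claim about small changes stands for the pre versus 12-month time effect.

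**What to change.** In Protocol II.C:
- Label 0.017 and 0.023 as variance shares, not changes in responses.
- Limit the claim about small changes to the pre versus follow-up time effect.
- State the assumed distribution of hours, including non-completers' hours and who is expected to be followed at one year. Give the dosage test's detectable full-course benefit as a range under it.
- Update that range once the observed spread of hours is known, which needs no outcome data.

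In SAP Step 5, add that a non-significant dosage slope is not evidence of no benefit.

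The cost is wording in both documents and one recalculation, with no extra enrolment. The drawback is that the stated sensitivity becomes less favourable.

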## IV. Data Analysis

### A. Data analysis

To examine the research questions, a repeated measures design will be used. The within-subjects factor will be the time of measurement (pre-survey and 12-month follow-up survey), and the between-subjects factor will be the format of the SSHF curriculum (standard or compressed) and support services.

Descriptive statistics will be computed to summarize the demographic variables and the variables of interest. Shapiro-Wilk tests will be conducted to assess the normality of the data. If the data are not normally distributed, appropriate transformations will be applied, or nonparametric tests will be used. To examine the first research question, a repeated measures analysis of variance (ANOVA) will be conducted with partner relationship attitudes as the dependent variable. The between-subjects factor will be the format of the SSHF curriculum, and the within-subjects factor will be time of measurement. If significant main effects or interactions are found, post hoc tests (e.g., Bonferroni) will be conducted to examine the pairwise comparisons.

The same approach will be used for the remaining research questions, with sexual attitudes, partner relationship behavior, financial attitudes, and employment attitudes as dependent variables. The level of statistical significance will be set at  $p < 0.05$ . Effect sizes will be reported using partial eta-squared ( $\eta^2$ ), which provides an estimate of the proportion of variance in the dependent variable accounted for by each factor in the ANOVA.

To examine the reliability of the scales, Cronbach's alpha will be computed for each construct. A value of 0.70 or higher will indicate acceptable reliability. To examine the validity of the scales, confirmatory factor analysis (CFA) will be conducted to test the hypothesized factor structure of each construct. If the hypothesized factor structure does not fit the data well, exploratory factor analysis (EFA) will be conducted to identify the underlying factor structure. Missing data will be handled using multiple imputation techniques to minimize bias and increase power. Overall, this study will use a repeated measures design with ANOVA to examine the effects of the SSHF curriculum on various domains of relationship and personal functioning and will use reliability and validity analyses to ensure the psychometric properties of the measures.

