To measure the impact of dosage in hours on change in pre to post-survey, a regression analysis will be conducted. Specifically, a multiple regression analysis will be conducted with dosage in hours as the predictor variable and change in the dependent variables (partner relationship attitudes, sexual attitudes, partner relationship behavior, financial attitudes, and employment attitudes) as the outcome variables. The model will control for the format of the SSHF curriculum and support services, as well as any demographic variables that are significantly related to the outcome variables.

Assumptions of linear regression, such as normality of residuals, homoscedasticity, and linearity, will be checked using diagnostic plots and statistical tests, such as the Shapiro-Wilk test for normality and the Breusch-Pagan test for homoscedasticity. If the assumptions are violated, appropriate transformations or non-parametric tests will be used. Additionally, the potential for multicollinearity among the predictor variables will be assessed using variance inflation factor (VIF) values. A VIF value greater than 10 indicates problematic multicollinearity, and steps will

be taken to address this issue, such as excluding highly correlated predictor variables. Overall, this study will use regression analysis to examine the relationship between dosage in hours and change in the dependent variables, while controlling for relevant covariates

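### The printed minimum detectable effects (0.017 and 0.023) do not follow from the two-tailed test the protocol describes and do not describe the one-degree-of-freedom tests in the SAP

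*Protocol*

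**What the plan says.** Protocol II.C (Sample, Power analysis) bases the calculation on a linear regression, described as "a model that compares the relative influences of participant characteristics as predictor that is regressed against a series of dependent variables". The table has two rows, "Post-test 1105 0.017" and "Follow-up 774 0.023". The text below it gives the error rates, "These power analyses assume an Alpha Level of 0.05 with a two-tailed test and power level set at 0.80", and the yardstick, "small effect sizes <0.02 and medium effect sizes <0.15". It concludes that "the proposed research design is demonstrated to measure large, medium, and small changes" in participants' responses. The effect metric is not named and no number of predictors appears in this section.

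SAP IV.A tests R1 with a repeated-measures ANOVA: "The within-subjects factor will be the time of measurement (pre-survey and 12-month follow-up survey"). The between-subjects factor is format, standard or compressed. R2-R5 follow the same approach. For dosage, "a multiple regression analysis will be conducted with dosage in hours as the predictor variable". The prose applies this regression to the pre-to-post change, while the model specification table lists follow-up dependent variables. Step 5 of the SAP treats a significant dosage coefficient as confirming a hypothesis.

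**The concern.** The sidedness, alpha and power in the protocol define a test of a single coefficient, and the printed effects are too large for that test at these sample sizes. They look like the output of a joint F-test of many predictors, which has no tails. Each SAP test that bears on R1-R5 has one numerator degree of freedom, so the table describes none of them.

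Interpretation is what suffers. Table 3's hypotheses are called confirmatory and R3 is the primary outcome. A null one-year result can be read only if the detectable mean change is known. The share of variance explained by a set of participant characteristics does not supply it, so the closing sentence of the power paragraph lacks support.

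**Working it through.** **Inputs.** From Protocol II.C: N=1105 and 774; printed effects 0.017 and 0.023; alpha 0.05 two-tailed; power 0.80. The 0.02 and 0.15 benchmarks belong to the f² scale. From SAP IV.A: two levels of time, two of format, and one continuous dosage variable, so each test has 1 df.

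**Method.** Noncentral F with u numerator df, v = N−u−1 denominator df and noncentrality λ = f²·N, solved for f² at power 0.80.

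**Step 1: try to reproduce the table.**

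| Predictors tested jointly | f², N=1105 | f², N=774 |
|---|---|---|
| printed | 0.017 | 0.023 |
| 1 | 0.0071 | 0.0102 |
| 12 | 0.0158 | 0.0227 |
| 13 | 0.0163 | 0.0234 |
| 14 | 0.0168 | 0.0241 |
| 15 | 0.0172 | 0.0247 |

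The first row needs 14 or 15 predictors and the second 12 or 13. No one count gives both to three decimals, but the miss is at rounding level: 13 predictors fall short of the first row by about 0.0002. Read as R², 14 predictors give 0.016499 and 0.023498.

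Scales that shrink as 1/√N (standardized differences, correlations) do not explain the table. They imply a ratio between rows of √(1105/774) = 1.20. The printed ratio is 0.023/0.017 = 1.35, or 1.29 to 1.42 allowing for rounding.

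**Step 2: one-coefficient test.** As a hand check, λ ≈ (1.960+0.842)² = 7.85, so f² ≈ 7.85/1105 = 0.0071 and 7.85/774 = 0.0101 (exact 0.0102). The printed values are 0.017/0.0071 = 2.4 and 0.023/0.0102 = 2.3 times these. At the printed effects a 1-df test has power 0.991 and 0.988, and 80% power would need only 464 and 344 participants. Adding covariates to the model leaves these figures essentially unchanged.

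**Step 3: one-year time effect, N=774.** For a paired change dz = √f² = √0.0102 = 0.101, whereas f²=0.023 would imply √0.023 = 0.152. In outcome SDs the detectable change is dz·√(2(1−ρ)). The documents give no baseline to 12-month correlation. Assuming ρ from 0.7 to 0.3, it is 0.08 to 0.12 SD.

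**Step 4: format-by-time, N=774.** The detectable difference between formats, in SDs of change, is 2.802/√(774·p(1−p)), with p the share in one format. No split is stated in the text available. For illustration, compare it with what f²=0.023 implies, √(0.023/(p(1−p))):

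| Assumed split | Detectable | Implied by 0.023 |
|---|---|---|
| 50:50 | 0.20 | 0.30 |
| 90:10 | 0.34 | 0.51 |

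At either split the test detects less than the printed figure implies.

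**The case against.** The strongest reply is that nothing is lost. Every 1-df test detects smaller effects than printed, two-tailed may be loose wording, and the study calls itself descriptive. This stands in part: the error is conservative, and it calls for no change to the sample.

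Two further replies also limit the point. The predictor count may sit in text not available here, since the SAP extract begins at Step 4. And the protocol says its regression also quantifies the benefits of participation, so it belongs to the same family of models as the SAP's Steps 4 and 5. The mismatch is therefore in the effect tested and its degrees of freedom. It would be too much to say that the powered model has nothing to do with R1-R5.

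Three stronger readings are tempting, and the documents support none of them:

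- A reader might infer that the trial is underpowered. Under independence the calculation points the other way.
- A reader might infer that the format comparison is weaker than the table suggests, because 0.20 or 0.34 SD exceeds 0.10. That sets a two-group difference against a paired change. On the f² scale both tests have the same 0.0102.
- A reader might infer a serious inconsistency from the lack of a single predictor count that fits both rows. The gap is rounding. R² with 13 predictors, rounded upward, gives both rows, and the documents do not say that both waves use one model.

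None of this rescues the stated figures as results for a two-tailed test.

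**Conclusion.** Wrong as written, with a modest consequence. The printed effects are 2.3 to 2.4 times those of the test described, and they do not describe the SAP's tests of R1-R5. The statement that the design has been shown to measure changes of every size does not follow from the calculation given.

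The replacement figures rest on assumptions to be stated with them:

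- Youth are independent, as in the protocol's own table, although delivery is in school workshops or retreats. A design effect of about 2.3 to 2.4 would use up the conservative margin; the text available gives no intraclass correlation.
- There is no multiplicity adjustment.
- The 0.10 is the change averaged over participants. If the ANOVA weights the two formats equally, the figure is half the format-by-time one: 0.20/2 = 0.10 at 50:50 and 0.34/2 = 0.17 at 90:10.
- N=774 applies only to outcomes measured at one year. Protocol Table 8 lists only OLLE then, while Table 6 takes the R1-R3 items from nFORM.

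**What to change.** Name the effect metric and replace the two-row table with one row per SAP test:

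1. One-year time effect, 1 df, N=774: dz = 0.10.
2. Slope on hours, 1 df: partial f² = 0.0071 at N=1105 and 0.0102 at N=774.
3. Format-by-time, 1 df: computed for the planned split (about 0.20 SD of change at an assumed 50:50).

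If the regression on participant characteristics is kept, give it its own row, labelled as an omnibus F-test, with its predictor count and without the two-tailed wording. State below the table that the figures assume independent youth, and for which outcomes the one-year N holds. Rewrite the closing sentence around the detectable one-year change.

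The cost is one table and one paragraph. Sample, data collection and schedule are unaffected.
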